Type 3b	 Overt bleeding plus hemoglobin drop ≥5** g/dL (provided hemoglobin drop is related to bleed) Cardiac tamponade Bleeding requiring surgical intervention for control (excluding dental / nasal / skin / hemorrhoid) Bleeding requiring intravenous vasoactive agents 		
Type 3c	 Intracranial hemorrhage (does not include microbleeds or hemorrhagic transformation; does include intraspinal) Subcategories: confirmed by autopsy or imaging or LP Intra-ocular bleed compromising vision 		
Type 4	 CABG-related bleeding Perioperative intracranial bleeding within 48 hours Reoperation following closure of sternotomy for the purpose of controlling bleeding Transfusion of ≥ 5 units of whole blood or packed red blood cells within 48 hour period* Chest tube output ≥ 2 L within a 24 hour period 		
Type 5a	Probable fatal bleeding; no autopsy or imaging confirmation, but clinically suspicious		
Type 5b	Definite fatal bleeding: overt bleeding or autopsy or imaging confirmation		

Obs: Platelet transfusions should be recorded and reported, but are not included in these definitions until further information is obtained about the relationship to outcomes.

* Cell saver products will not be counted.

** Corrected for transfusion (1 unit PRBC or 1 unit of whole blood = 1 g/dL Hgb)

CEREBROVASCULAR ACCIDENT (CVA) (See STROKE)

- Ischemic stroke (cerebral infarction); or
- Hemorrhagic stroke (intracerebral hemorrhage or subarachnoid hemorrhage).

CORONARY ARTERY BYPASS GRAFT SURGERY (CABG)

Acute CABG is defined as immediate transfer from the cath lab to the operative room for emergent bypass surgery during the initial treatment phase.

CABG during follow-up is only considered as a clinical-indicated Target Lesion Revascularization if coronary angiography indicates a diameter of stenosis greater than 50% of the stented coronary segment associated with one of the following conditions:

- A positive history of recurrent angina pectoris presumably related to the target vessel.
- Objective signs of ischemia (exercise test or equivalent) presumably related to the target vessel.
- Abnormal results of any invasive functional diagnostic test (e.g. Doppler flow velocity reserve, fractional flow reserve).

DEATH (per ARC definition, Circulation 2007;115:2344-51)

All deaths are considered cardiac unless an unequivocal non-cardiac cause can be established. Specifically, any unexpected death even in patients with coexisting potentially fatal non-cardiac disease (e.g. cancer, infection) should be classified as cardiac.

Cardiac death:

Any death due to proximate cardiac cause (e.g. MI, low-output failure, fatal arrhythmia), unwitnessed death and death of unknown cause, all procedure related deaths including those related to concomitant treatment.

Vascular death:

Death due to non-coronary vascular causes such as cerebrovascular disease, pulmonary embolism, ruptured aortic aneurysm, dissecting aneurysm, or other vascular cause.

Non-cardiovascular death:

Any death not covered by the above definitions such as death caused by infection, malignancy, sepsis, pulmonary causes, accident, suicide or trauma.

DEVICE DEFICIENCY

See Section 14 for definition of device deficiency.

DIABETES MELLITUS (DM)

History of diabetes mellitus. The condition will be further categorized as treated by diet, oral hypoglycemic medications, or insulin.

DISSECTION

NHLBI Dissection Classification System:

- Grade A: Minor radiolucencies within the lumen during contrast injection with no persistence after dye clearance.
- Grade B: Parallel tracts or double lumen separated by a radiolucent area during contrast injection with no persistence after dye clearance.

- Grade C: Extraluminal cap with persistence of contrast after dye clearance from the lumen.
- Grade D: Spiral luminal filling defects.
- Grade E: New persistent filling defects.
- Grade F: Non-A-E types that lead to impaired flow or total occlusion.

Note: Grade E and F dissections may represent thrombus.

DISTAL EMBLOIZATION

Distal embolization is defined as new abrupt cut off or filling defect distal to the treated lesion.

IN-STENT RESTENOSIS - MEHRAN CLASSIFICATION [20]

- Class I: Focal ISR group. Lesions are ≤10 mm in length and are positioned at the unscaffolded segment (i.e., articulation or gap), the body of the stent, the proximal or distal margin (but not both), or a combination of these sites (multifocal ISR);
- Class II: "Diffuse intra-stent" ISR. Lesions are >10 mm in length and are confined to the stent(s), without extending outside the margins of the stent(s).
- Class III: "Diffuse proliferative" ISR. Lesions are >10 mm in length and extend beyond the margin(s) of the stent(s).
- Class IV: ISR with "total occlusion." Lesions have a TIMI flow grade of 0.

MAJOR EPICARDIAL VESSELS

- Left anterior descending artery (LAD) with septal and diagonal branches;
- Left circumflex artery (LCX) with obtuse marginal and/or ramus intermedius branches;
- Right coronary artery (RCA) and any of its branches.

MAJOR ADVERSE CARDIAC EVENTS (MACE)

The composite rate of cardiac death, any MI or ischemia-driven TLR

MINIMUM LUMEN DIAMETER (MLD)

MLD is defined the average of two orthogonal views (when possible) of the narrowest point within the area of assessment – in lesion, in stent or in segment. MLD is visually estimated during angiography by the Investigator; it is measured during QCA by the Angiographic Core Laboratory.

MYOCARDIAL INFARCTION (MI)

Post-PCI (Type 4a) and post-CABG (Periprocedural) Mis (Type 5):

Periprocedural MIs will be defined based on the SCAI definitions [21] as follows:

²⁰ Mehran R, Dangas G, Abizaid AS, et al. Angiographic patterns of In-stent restenosis: Classification and implications for long-term outcome. Circulation. 1999. **100**: p. 1872-78.

- In patients with normal baseline CK-MB: The peak CK-MB measured within 48 hours of the procedure rises to ≥10x the local laboratory ULN, or to ≥5x ULN with new pathologic Q-waves in ≥2 contiguous leads or new persistent LBBB, OR in the absence of CK-MB measurements and a normal baseline cTn, a cTn (I or T) level measured within 48 hours of the PCI rises to ≥70x the local laboratory ULN, or ≥35x ULN with new pathologic Q-waves in ≥2 contiguous leads or new persistent LBBB.
- 2) In patients with elevated baseline CK-MB (or cTn) in whom the biomarker levels are stable or falling: The CK-MB (or cTn) rises by an absolute increment equal to those levels recommended above from the most recent pre-procedure level.
- 3) In patients with elevated CK-MB (or cTn) in whom the biomarker levels have not been shown to be stable or falling: The CK-MB (or cTn) rises by an absolute increment equal to those levels recommended above *plus* new ST-segment elevation or depression *plus* signs consistent with a clinically relevant MI, such as new onset or worsening heart failure or sustained hypotension.

In addition the following additional definitions will be used to assess peri-procedural MIs for the purpose of sensitivity analyses:

- The Universal Definition of MI definition (JACC Vol. 60, 2012)
- A modification of the SCAI definition of periprocedural MI that utilizes a threshold CK-MB of ≥5x ULN (rather than ≥10x) in subjects with a normal baseline CK-MB without a requirement for associated clinical signs or symptoms
- A modification of the SCAI definition of periprocedural MI that utilizes a threshold CK-MB of ≥3x (rather than ≥10x) in subjects with a normal baseline CK-MB without a requirement for associated clinical signs or symptoms

Spontaneous MI (MI Type I):

Spontaneous MI (MI Type I) will be defined based on the Universal Definition of Myocardial Infarction [22] as follows:

Symptoms suggestive of ischemia/infarction in association with ECG, cardiac biomarker or pathologic evidence of infarction as follows:

- Detection of a rise and/or fall of cardiac biomarker values (preferably cardiac troponin T or I) with at least one value above the 99th percentile upper reference limit and with at least one of the following:
- Symptoms of ischemia

²¹ Moussa, ID, et al. Consideration of a new definition of clinically relevant myocardial infarction after coronary revascularization an expert consensus document from the society for cardiovascular angiography and interventions (SCAI). Catheter Cardiovasc Interv, 2013.

²² Thygesen, K, et al. Third universal definition of myocardial infarction. J Am Coll Cardiol, 2012. **60**(16): p. 1581-98.

- New or presumed new significant ST segment-T wave (ST-T) changes or new LBBB
- Development of new Q waves in the ECG
- Imaging evidence of new loss of viable myocardium or new regional wall motion abnormality
- Identification of an intracoronary thrombus by angiography or autopsy

Spontaneous MI typically occurs after the periprocedural period and may be secondary to late stent complications or progression of native disease (e.g., non-culprit lesion plaque rupture). Performance of ECG and angiography supports adjudication to either a *target* or *non-target vessel or lesion* in most cases.

NO-REFLOW

An acute reduction in coronary flow (TIMI grade 0-1) in the absence of dissection, thrombus, spasm, or high-grade residual stenosis at the original target lesion. Also see 'Acute Closure'.

PERCENT DIAMETER STENOSIS (%DS)

The value calculated as 100 * (1 - MLD/RVD) using the mean values from two orthogonal views (when possible) by QCA.

PERCUTANEOUS CORONARY INTERVENTION (PCI)

Refers to all interventional cardiology methods for treatment of coronary artery disease.

PERFORATION

Perforations will be classified as follows:

- Angiographic perforation: perforation detected by the clinical site or the core laboratory at any point during the procedure.
- Clinical perforation: perforation requiring additional treatment (including efforts to seal the perforation or pericardial drainage), or resulting in significant pericardial effusion, abrupt closure, myocardial infarction, or death.
- Pericardial hemorrhage/tamponade: perforation resulting in cardiac tamponade.

PERSISTING DISSECTION

Dissection at follow-up that was present post baseline procedure.

PRIMARY INVESTIGATOR

The physician responsible for conducting the clinical trial at each investigational site.

PRINCIPAL INVESTIGATOR

A physician-specialist, related to the trial, who is responsible for the overall conduct of the trial at all sites and compliance with clinical investigation plan and relevant regulations.

PROTOCOL DEVIATIONS - MAJOR

Major protocol deviations include, but are not limited to, enrollment of a subject:

• whose informed consent was not properly obtained

- who did not meet all of the inclusion or exclusion criteria
- who did not receive the study stent
- who did not receive at least 12 months of DAPT post baseline procedure

REFERENCE VESSEL DIAMETER (RVD)

Average diameter of proximal and distal healthy segments by QCA. 10 mm "normal" reference segments are selected proximal and distal to the stenosis and averaged to define the reference vessel diameter. A computer-defined interpolated normal segment will be used to calculate percent diameter stenosis.

RESTENOSIS

Re-narrowing of the artery following the removal or reduction of a previous narrowing.

REVASCULARIZATION (per ARC definition, Circulation 2007;115:2344-51)

Target Lesion Revascularization (TLR)

TLR is defined as any repeat percutaneous intervention of the target lesion or bypass surgery of the target vessel performed for restenosis or other complication of the target lesion. All TLR should be classified prospectively as clinically indicated (CI) or not clinically indicated by the investigator prior to repeat angiography. An independent Angiographic Core Laboratory should verify that the severity of percent diameter stenosis meets requirements for clinical indication and will overrule in cases where investigator reports are not in agreement. The target lesion is defined as the treated segment from 5 mm proximal to the stent and to 5 mm distal to the stent.

Target Vessel Revascularization (TVR)

TVR is defined as any repeat percutaneous intervention or surgical bypass of any segment of the target vessel). The target vessel is defined as the entire major coronary vessel proximal and distal to the target lesion, which includes upstream and downstream branches, and the target lesion itself.

Non Target Lesion Revascularization (Non-TLR)

Any revascularization in the target vessel for a lesion other than the target lesion is considered a non-TLR.

Non Target Vessel Revascularization (Non-TVR)

Any revascularization in a vessel other than the target vessel is considered a non-TVR.

Clinically Driven Revascularization (TLR/TVR)

Revascularization at the target site (TLR) or in the target vessel (TVR) that is associated with:

- A positive functional ischemia study or ischemic symptoms; AND angiographic lumen minimal lumen diameter stenosis ≥50% by QCA; OR
- A TLR or TVR with a diameter stenosis \geq 70% by QCA without either angina or a positive functional study.

SERIOUS ADVERSE DEVICE/DRUG EFFECT

See Section 14 for definitions of adverse device/drug effects (serious, anticipated, and unanticipated)

SERIOUS ADVERSE EVENT (SAE)

See Section 14 for definitions of adverse events (non-serious and serious)

STENT THROMBOSIS (per ARC definition, Circulation 2007;115:2344-51)

Stent Thrombosis should be reported as a cumulative value at the different time points and with the different separate time points. Time 0 is defined as the time point after the guiding catheter has been removed and the patient left the catheterization lab after the baseline procedure.

Timing	Acute	\leq 24 hours post stent implantation	
	Subacute	> 24 hours to 30 days post stent implantation	
	Late	> 30 days to 1 year post stent implantation	
	Very late	> 1 year post stent implantation	
Туре	Primary	Occurs in target lesion or margins after baseline procedure	
	Secondary	Occurs after revascularization (TLR, TVR, or non-TVR)	
Category	Definite	Definite stent thrombosis is confirmed by either angiographic* or pathologic [†] analysis	
	Probable	Probable stent thrombosis is considered to have occurred after intracoronary stenting for	
		either:	
		• any unexplained death within the first 30 days unless that patient had baseline procedure for ST elevation MI	
		• any MI, irrespective of time after baseline procedure, that is related to documented acute ischemia in the territory of the implanted stent without angiographic confirmation of stent thrombosis and in the absence of any other obvious cause	
	Possible	Possible stent thrombosis is considered to have occurred with any unexplained death from 30 days after intracoronary stenting until end of trial follow-up	

*Angiographic confirmation of stent thrombosis

The presence of an intracoronary thrombus that originates in the stent or in the segments 5 mm proximal or distal to the stent and presence of at least one of the following criteria within a 48-hour time window:

- Acute onset of ischemic symptoms at rest The incidental angiographic documentation of stent occlusion in the absence of clinical signs or symptoms is not considered a confirmed stent thrombosis (silent occlusion)
- New ischemic ECG changes that suggest acute ischemic
- Typical rise and fall in cardiac biomarkers (refer to spontaneous MI definition)
- Intracoronary thrombus is defined as a spheric, ovoid, or irregular noncalcified filling defect or lucency surrounded by contrast material on 3 sides or within a coronary stenosis seen in multiple projections, or persistence of contrast material within the lumen, or a visible embolization of intraluminal material downstream.
- Nonocclusive or occlusive thrombus
- TIMI 0 or TIMI 1 intrastent or proximal to a stent up to the most adjacent proximal side branch or main branch if originates from the side branch.

[†]Pathological confirmation of stent thrombosis

Evidence of recent thrombus within the stent determined at autopsy or via examination of tissue retrieved following thrombectomy.

STROKE

Stroke is defined as the sudden onset of vertigo, numbness, dysphasia, weakness, visual field defects, dysarthria, or other focal neurological deficits due to vascular lesions of the brain such as hemorrhage, embolism, thrombosis, or rupturing aneurysm, that persists >24 hours.

SUBINVESTIGATOR

A physician-member of a clinical study team who administers investigational products, used in the clinical trial, to a subject.

SUCCESSFUL PRE-DILATION

Pre-dilation has been successfully completed without complications if all of the following apply:

- Diameter stenosis < 50%
- TIMI Grade III flow
- Lesion length still within the requirements of the protocol
- No angiographic complications or prolonged chest pain

TARGET LESION

Lesion that has met the angiographic inclusion and exclusion criteria and that is to be treated during the baseline procedure.

TARGET LESION FAILURE (TLF)

The composite rate of cardiac death, target-vessel MI or ischemia-driven TLR

TARGET VESSEL

The entire epicardial vessel in which the treated lesion is located.

TARGET VESSEL FAILURE (TVF)

The composite rate of death, target vessel-related MI or ischemia-driven TVR

TIMI FLOW GRADES

- 0. No contrast flow through the stenosis.
- 1. A small amount of contrast flows through the stenosis but fails to fully opacify the artery beyond.
- 2. Contrast material flows through the stenosis to opacify the terminal artery segment. However, contrast enters the terminal segment perceptibly more slowly than more proximal segments. Alternatively, contrast material clears from a segment distal to a stenosis noticeably more slowly than from a comparable segment not preceded by a significant stenosis.
- 3. Anterograde flow into the terminal coronary artery segment through a stenosis is as prompt as anterograde flow into a comparable segment proximal to the stenosis. Contrast material clears as rapidly from the distal segment as from an uninvolved, more proximal segment.

VASCULAR COMPLICATIONS

These may include access-site hematoma, pseudoaneurysm, arteriovenous fistula, peripheral ischemia or nerve injury.

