4.6 Steps to Control or Mitigate Risks

Subjects with no aspirin resistance, allergy, or bleeding risk will continue on aspirin indefinitely and either clopidogrel (75 mg/day), or prasugrel (2.5-3.75 mg/day) for a minimum of 12 months following stent implantation according to national guidelines and standard of care unless an intervening medical necessity occurs such as severe bleeding, in accordance with the PCI recommendations from ACCF/AHA/SCAI [1] and the elective PCI guidelines from JCS [8]. If DAPT is discontinued before 12 months due to medical necessity (for example, severe bleeding) the reason should be documented.

The investigational plan is specifically designed to manage and minimize risks through careful subject selection, thorough training of investigators, adherence to the pre-determined time points to assess subject clinical status and regular clinical monitoring visits by Sponsor appointed monitoring personnel.

In addition, an independent Data Safety Monitoring Board (DSMB) will monitor safety of the subjects throughout the trial.

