2. In-clinic visit at 1-year follow-up and ECG may be waived if subject refuses to return to clinic or is unable to return. A telephone visit should then be conducted in lieu of a clinic visit.

3. Lipid profile is strongly recommended.

- 4. Within 24 hours pre-procedure. For subjects with ACS, enzyme levels need to be within 8 hours of the procedure or have already been shown to be decreasing. For subacute STEMI patients enzyme levels must have peaked for either CK-MB or Troponin (I or T) or both. High sensitivity troponin assays (hsTrop) are acceptable if non-hsTrop and CK-MB are not available at the local hospital.
- 5. If Troponin is elevated or CK-MB is elevated ≥ upper limit of normal, serial measurements of CK and CK-MB (preferred) or Troponin (I or T) must be done until a decline is noted
- 6. CK and CK-MB or Troponin (I or T) and ECG should be obtained for all suspected ischemic events. CK-MB is preferred but at sites where CK-MB is not available Troponin I or T may be used.
- 7. Clopidogrel 75 mg daily or prasugrel 2.5 to 3.75 mg daily must be given for a minimum of 12 months according to national guidelines and standard of care as well as aspirin 81 to 100 mg daily to be taken indefinitely.
- 8. Concomitant cardiac medications will be recorded by categories (e.g., statin, non-statin lipid lowering, ACE inhibitors, ARBs, beta-blockers, calcium channel blockers, other anti-anginals).
- 9. Adverse events that occur after informed consent has been obtained will be recorded.

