6.4.9.3 Post-Procedure Anti-Platelet Medication

Dual anti-platelet therapy should be instituted post procedure in all patients as shown in Error! Reference source not found.7. All subjects are required to have clopidogrel/prasugrel administration for a minimum of 12 months according to national guidelines (Guidelines for elective percutaneous coronary intervention in patients with stable coronary disease (JCS 2011) [8]) and standard of care as well as aspirin administration indefinitely unless an intervening medical necessity occurs such as severe bleeding.

Agent	Instructions
Clopidogrel	All subjects who receive a study stent will be treated for a minimum of twelve months of clopidogrel (75 mg/day) according to national guidelines and standard of care. At least 12 months following stent implantation is recommended per the JCS guidelines for elective percutaneous coronary intervention [8].
OR Prasugrel	Prasugrel 3.75 mg/day can be used in place of clopidogrel at the investigator's discretion. In subjects considered to require dose reduction by their conditions (body weight (<50 kg), age, renal function, and other risks), prasugrel should be given at a dose of 2.5 mg/day.
Aspirin	Subjects with no aspirin resistance, allergy, or bleeding risk should continue on aspirin (minimum of 81 mg/day and up to 162 mg/day or dose per standard hospital practice) indefinitely, in accordance with the JCS PCI recommendations and the JCS guidelines. Low-dose aspirin ($\leq 100 \text{ mg/day}$) is preferred in all patients.

 Table 7: Post-Procedure Anti-Platelet Medication Regimen

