10.3 Notification Requirements and Time Frames

Major protocol deviations shall be notified to the trial Sponsor and Ethics Committee. Sponsor nominated personnel will also observe and record any protocol deviations during routine monitoring visits and follow up accordingly.

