6.3. PER PROTOCOL SET [PPS]

The Per Protocol Set (PPS) will contain all patients who receive the study stent with no major protocol violations. Major protocol violations include enrollment of a patient:

- · whose informed consent was not properly obtained
- who did not meet all of the inclusion or exclusion criteria
- who did not receive the study stent due to any reason
- who did not receive at least 12 months of Dual Antiplatelet Therapy (DAPT) post baseline procedure. Details of DAPT to be received post-procedure are given in Section 6.4.9.3 of the protocol.

Major protocol violations leading to exclusion from the PPS will be summarized using the FAS.

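### As written, the 12-month DAPT rule for the per-protocol set also removes patients who die on DAPT, including cardiac deaths that are primary-endpoint events

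*Protocol*

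**What the plan says.** **The rule.** Protocol 21.1, under major protocol deviations, lists enrolment of a subject "who did not receive at least 12 months of DAPT post baseline procedure". SAP 6.3 lists a patient "who did not receive at least 12 months of Dual Antiplatelet Therapy (DAPT) post baseline procedure" among the violations that exclude from the PPS, and adds: "Details of DAPT to be received post-procedure are given in Section 6.4.9.3 of the protocol". Neither bullet mentions death or a permitted early stop.

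**What the treatment sections allow.** Protocol 4.6 sets a 12-month minimum subject to medical necessity and adds: "If DAPT is discontinued before 12 months due to medical necessity (for example, severe bleeding) the reason should be documented". Protocol 6.4.9.3 requires 12 months of clopidogrel or prasugrel "as well as aspirin administration indefinitely unless an intervening medical necessity occurs such as severe bleeding". The natural reading applies that exception to the whole regimen, though by grammar it could attach to aspirin alone.

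**Where the rule is used.** SAP 15.1.3 repeats the primary analysis on the PPS. It is the only sensitivity analysis of the primary endpoint, because SAP 4.3 drops the one based on alternative definitions of myocardial infarction. SAP 6.2 keeps patients with major deviations in the FAS. Protocol 10.3 says: "Major protocol deviations shall be notified to the trial Sponsor and Ethics Committee".

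**The concern.** A patient who dies in month 4 while taking DAPT as prescribed has not received 12 months of it. The SAP 6.3 bullet, taken as written, excludes that patient from the PPS. If the death is cardiac, it is a component of target lesion failure (SAP 15.1.1). The patient is then removed because the endpoint occurred, not because of how treatment was delivered. Each such removal lowers the JNIR failure rate, which favours a finding of non-inferiority.

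At stake is the credibility of the single analysis meant to support the primary result. A smaller matter is deviation reporting: the same words in Protocol 21.1 would classify a death on DAPT as a major deviation. They also leave unclear whether a bleeding-related stop handled as Protocol 4.6 describes is one.

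**Working it through.** **1. Who is removed from the PPS by dying.** SAP 15.1.2 includes in the primary analysis only patients followed to at least day 335 or with a primary-endpoint event by day 379. A non-cardiac death before day 335 without a prior event is therefore already outside the analysis. So deaths before day 335 that are in the FAS analysis and would be lost from the PPS are patients counted as failures.

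**2. Effect on the JNIR rate.** Inputs: 95 evaluable patients (100 less 5% loss, Protocol 7.5) and an assumed 6 events, close to the planned 5.8%.
- No removal: 6/95 = 6.32%.
- One cardiac death removed: 5/94 = 5.32%, a fall of 1.00 point.
- Two removed: 4/93 = 4.30%, a fall of about 2.0 points.

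The margin is 5 points.

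**3. Effect on the test.** Assumptions: 22 events in 380 matched controls (5.79%, the planned rate at 4:1). After one JNIR cardiac death is removed, 4:1 matching is kept and the controls are 22/376. The SAP's printed statistic is

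τ = (p_J − p_B − 0.05) / √[p_J(1−p_J)/n_J + p_B(1−p_B)/n_B],

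tested one-sided at 0.10.

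Worked case, starting from 7/95:
- Before: (0.0737 − 0.0579 − 0.05)/0.0294 = −1.165, p = 0.122.
- After, 6/94: (0.0638 − 0.0585 − 0.05)/0.0280 = −1.598, p = 0.055.

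The standard Farrington-Manning variance uses rates constrained to differ by exactly the margin. It gives:
- Before: constrained rates 0.1038 and 0.0538, standard error 0.0334, p = 0.153.
- After: constrained rates 0.1032 and 0.0532, standard error 0.0334, p = 0.091.

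Neighbouring starting counts, by the same formulas:

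| JNIR before → after | Printed statistic, p | Constrained variance, p | Crosses 0.10? |
|---|---|---|---|
| 6/95 → 5/94 | 0.053 → 0.017 | 0.089 → 0.048 | No, passes both times |
| 7/95 → 6/94 | 0.122 → 0.055 | 0.153 → 0.091 | Yes |
| 8/95 → 7/94 | 0.222 → 0.126 | 0.240 → 0.156 | No, fails both times |

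Of these three starting counts, only the middle one changes the PPS conclusion.

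**4. Early stops for medical necessity.** The direction here is not fixed. From 6/95 = 6.32%, with 1 to 10 assumed stops excluded:
- all event-free: 6/94 = 6.38% to 6/85 = 7.06% (up 0.07 to 0.74 points);
- one with an event: 5/94 = 5.32% to 5/85 = 5.88% (down 1.00 to 0.43 points).

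**The case against.** The strongest reply is that Protocol 10.2 defines a deviation as a failure to follow the plan's requirements. A patient stopped for severe bleeding with the reason recorded, or one who dies on treatment, has failed nothing, so there is no deviation for 21.1 to grade. The SAP bullet also sends the reader to 6.4.9.3, where the exception sits, and it lacks the any-reason wording of the stent bullet above it.

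Much of this stands for early stops. A reader might infer that the plan flatly contradicts itself and that every bleeding-related stop is a major deviation. The documents do not support that: they leave the handling arguable. Nor is excluding permitted stops an error in itself, since a sponsor may want a strict set showing outcome under the full regimen.

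The reply is weaker for deaths. SAP 6.3 gives its own list of exclusions, and its pointer concerns the regimen to be received; neither it nor 6.4.9.3 addresses death. SAP 17.6.3 explicitly sets deaths aside when computing visit compliance; SAP 6.3 has no such words. A strict full-regimen set is no reason to discard endpoint deaths.

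Safeguards also exist. Set membership is agreed before database lock (SAP 6), exclusions are summarised on the FAS (SAP 6.3) and deviations are listed (SAP 10). They make exclusions visible, but they leave the rule to case-by-case reading in an open-label, single-arm trial.

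**Conclusion.** The point holds as a gap in wording, and it is minor. Applied as written, SAP 6.3 lets the only sensitivity analysis of the non-inferiority test drop cardiac deaths. Each one dropped lowers the JNIR rate by about 1 point, and a single removal can cross the 0.10 threshold when the result is already close to it.

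This rests on assumed counts. The documents give no rate of deaths or early stops, so no probability of a changed PPS result can be stated. They also do not say whether the PPS criteria apply to the BIONICS controls; if control deaths were dropped too, the net shift would be smaller.

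A reader might infer that the trial's primary conclusion is at risk. It is not: the FAS analysis keeps major deviations, and no planned sample size, margin or error rate changes. The effect is confined to the PPS and to deviation reporting.

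**What to change.** In SAP 6.3 and Protocol 21.1, limit the criterion to DAPT stopped before the earlier of 12 months or death, without a documented medical necessity under Protocol 4.6 and 6.4.9.3. If the sponsor wants a strict full-12-month-DAPT set, define it separately under its own name, and still do not count death on DAPT as a violation. Settle this before set membership is agreed.

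The cost is one clause in each document. No new data are needed: Protocol 4.6 already asks for the reason for an early stop, SAP 17.6.1 lists stop dates and discontinuation reasons, and all deaths are adjudicated. The downside is that the PPS will include some patients with shorter DAPT. Stops without a documented medical necessity remain excluded, so selection on what happens after the procedure is reduced but not removed.
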